9.15 Clinical Laboratory Tests

Clinical laboratory assessments will be performed at visits specified in the Schedules of Study Assessments (Table 1 and Table 2). Any blood sampling that occurs during the IP infusion should be collected from the opposite arm. Post-infusion PK blood samples should not be drawn from the cannula that was used for the infusion. These samples can be drawn from the arm opposite the infusion or can be from a separate access point in the same arm as the infusion.

9.15.1 Sample Collection, Storage, and Shipping

Each patient will have blood drawn and urine collected for the blood and urine laboratory safety assessments as listed/described in the sections below and the Schedules of Study Assessments (Table 1 and Table 2), including hematology, chemistry, urinalysis, 24-hour urine analysis, urine cytology, anti-dystrophin antibody, anti-viltolarsen antibody, and viral antigen and antibody testing.

Blood draw volumes for patients will be 8.5 to 16 mL per day at Screening, Day 1, Weeks 3, 5, 9, 13, 17, 21, 25, 37, 48, and end of treatment, totaling up to approximately 135.5 mL over the course of the study. No more than 31.0 mL of blood will be drawn in a 4-week period.

For post-Screening urinalyses, patients will collect a first morning void urine sample on the date of the specified visit and bring it to the site according to the Schedules of Study Assessments (Table 1 and Table 2). Analysis of the sample will include urine dipstick protein to be performed at the site. An aliquot will also be sent to the central laboratory for urinalysis (see Table 3 for a list of the laboratory analytes that will be measured for all urinalyses, including the first morning void urinalysis).

If first morning void urine dipstick protein $\geq 2+$, urine protein to creatinine ratio (UPCR) ≥ 0.5 mg/mg, or UPCR $\geq 2 \times$ baseline, a first morning void urine dipstick protein will be repeated

within 1 week. If 1 or more of these criteria are met again on the repeat test, a 24-hour urine sample will be collected within 1 week of the results to assess protein and creatinine. Caregivers will be provided a diary to enter void times during the 24-hour collection period. When obtaining this 24-hour urine, the patient will be asked to urinate in the toilet immediately after waking up on the day of the test. This time will be recorded in the diary as the start time. Directions will be provided for collection throughout the test, and documentation of all subsequent voids will be recorded in the diary through the first sample immediately after awakening on the following morning, as close to 24 hours later as possible. Refer to [Section 11.12.1](#) for additional details on monitoring of renal function and urine analyses.

If serum cystatin C $\geq 1.5 \times$ baseline, or if serum creatinine $\geq 2 \times$ baseline and ≥ 0.3 mg/dL, the test will be repeated within 1 week of the results. Refer to Section 11.12.1 for additional details on monitoring of renal function and urine analyses.

Samples will be collected by a trained member of the study team unless otherwise noted. All blood and urine samples will be sent to the designated central laboratory for testing unless otherwise noted. The urine cytology samples will be collected predose at the site and sent to a local laboratory for analysis. The procedures for the collection, handling, and shipping of central laboratory samples will be specified in the Laboratory Manual. Clinical laboratory tests are listed in Table 3.

Table 3. Clinical Laboratory Tests

Hematology, Chemistry, Urinalysis (Screening, First Morning Void, and Postdose), 24-Hour Urine Analysis, and Urine Cytology – Safety Labs

- Hematology
 - Red blood cell count
 - Hemoglobin
 - Hematocrit
 - Reticulocyte count
 - Mean corpuscular volume
 - Mean corpuscular hemoglobin
 - Mean corpuscular hemoglobin concentration
 - WBC
 - White blood cell differential
 - Platelet count
 - Fibrinogen
 - Activated partial thromboplastin time

-
- Prothrombin international normalization ratio
 - Blood Chemistry
 - Sodium
 - Potassium
 - Chloride
 - Calcium
 - Inorganic phosphorus
 - BUN
 - Creatinine
 - Cystatin C
 - Aspartate aminotransferase
 - Alanine aminotransferase
 - Gamma-glutamyl transferase
 - Alkaline phosphatase
 - Haptoglobin
 - Lactate dehydrogenase/lactate dehydrogenase isozyme
 - Creatine kinase
 - Total bilirubin (direct/indirect)
 - Total protein
 - Albumin
 - Albumin to globulin ratio
 - Total cholesterol
 - Triglyceride
 - Blood glucose
 - C-reactive protein
 - Urinalysis (Screening, First Morning Void, and Postdose)
 - Glucose
 - Blood
 - Urobilinogen
 - Specific gravity
 - Osmolality
 - Urinary sediment (erythrocytes, white blood cells, casts, epithelium, crystals)
 - Protein (benzethonium chloride method)
 - Microalbumin
 - N-acetyl-beta-D-glucosaminidase
 - α 1-microglobulin
 - β 2-microglobulin
 - Creatinine
 - Protein to creatinine ratio
 - Protein osmolality ratio
 - Dipstick protein (to be performed by the site on the first morning void urine samples)
 - 24-Hour Urine Analysis
 - Protein (benzethonium chloride method)
 - Creatinine
-

- Urine cytology

BUN = blood urea nitrogen; WBC = white blood cell count.

9.15.2 Anti-Dystrophin Antibody

Anti-dystrophin antibody testing will be performed on serum blood samples collected predose during the visits specified in the Schedules of Study Assessments (Table 1 and Table 2).

9.15.3 Anti-Viltolarsen Antibody

Anti-viltolarsen antibody testing will be performed on serum blood samples collected predose during the visits specified in the Schedules of Study Assessments (Table 1 and Table 2).

9.15.4 Antigen and Antibody Testing

Antigen and antibody testing will be performed during the Screening assessment. The following tests will be performed: hepatitis B antigen, hepatitis C antibody, and HIV antibody.

9.16 Pharmacodynamics and Efficacy Assessments

9.16.1 Function and Strength

All function and strength testing will be performed by a trained site clinical evaluator (CE). The same CE should perform testing on the same patient throughout the study when possible. Instructions and further details on these tests can be found within the CE Manual.

The function and strength measures will be videotaped to ensure that they are being conducted properly and consistently by the CE, where possible and upon consent. The videotaping will only be used to standardize the assessment in the tests. The videos will be reviewed centrally by an experienced physiotherapist and will be compiled and stored confidentially in the video review portal in compliance with all International Organization for Standardization requirements and in compliance with data protection requirements. The video review does not affect the assessment results and adoption of the test data. The patient will be allowed to participate in the study if they meet all other criteria even if they do not agree to the recording or recording is not permitted at the site.

9.16.1.1 Muscle Strength Measured with Hand-held Dynamometer

Muscle strength will be measured for elbow extension, elbow flexion, knee extension, and knee flexion on the dominant side only using a hand-held dynamometer. The force generated for each

muscle strength measure will be documented in source documents and captured in the relevant eCRF.

9.16.1.2 Brooke Scale

The Brooke scale for upper limb has grades ranging from 1 to 6. Grade 1 is given to the patient who can keep both his arms by his sides in the starting position and is then able to abduct the arms fully so that both the arms are touching over the head. Grade 6 is given when the patient is unable to raise his hands to his mouth, and the hands show no functional usefulness.

9.16.1.3 Vignos Scale

The Vignos scale for lower limb has grades ranging from 1 to 10; 1 means that the patient is able to walk and climb stairs without assistance, while 10 means that the patient is bed-bound. Ambulant patients score 1 to 6 and non-ambulant patients score 7 to 10 on the Vignos scale.

9.16.1.4 Performance of Upper Limb

The PUL 2.0 was specifically developed for the assessment of upper limb function in DMD. The PUL 2.0 provides both a total score and sub-scores for the 3 domains (shoulder, middle, and distal) that in DMD are progressively involved with a proximal to distal gradient. The PUL 2.0 includes 22 items with an entry item to define the starting functional level. The 22 items are subdivided into the high level shoulder dimension (6 items), middle level elbow dimension (9 items), and distal wrist and hand dimension (7 items). For weaker patients, a low score on the entry item (0-2) means high level items do not need to be performed. Scoring options vary across the scale between 0-1 and 0-2 according to performance. Each dimension can be scored separately with a maximum score of 12 for the high level shoulder dimension, 17 for the middle level elbow dimension, and 13 for the distal wrist and hand dimension. A total score can be achieved by adding the 3 level scores (for maximum total score of 42).

9.16.1.5 North Star Ambulatory Assessment

NSAA will be performed by a CE at visits specified in the Schedules of Study Assessments ([Table 1](#) and [Table 2](#)). The NSAA is a clinician-rated, 17-item, functional scale originally designed for ambulant boys with DMD who are able to ambulate at least 10 meters ([Mazzone et al, 2009](#)). This evaluation tool assesses functional activities including standing,

getting up from the floor, negotiating steps, hopping, and running. The assessment is based on a 3-point rating scale of 2 = ability to perform the test normally, 1 = modified method or assistance to perform test, and 0 = unable to perform the test. Thus, total score can range from 0 (completely non-ambulant) to 34 (no impairment) on these assessments. The NSAA will include an assessment of both grade and time for the Time to Run/Walk 10 Meters Test and the Time to Stand Test. Individual test item scores and total score will be recorded in source documents and in the relevant eCRF. This test should take approximately 20 minutes.

9.16.1.6 Loss of Ambulation

Time to run/walk 10 meters will be assessed as part of the NSAA for patients performing the NSAA. Loss of ambulation will be defined as the inability to perform the Time to Run/Walk 10 Meters Test in ≤ 30 seconds at any post-baseline visit and for all remaining assessments.

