- s. To be performed on a predose urine sample collected on-site.
- t. To be performed on a urine sample collected within 5 hours after completion of infusion.
- u. To include hepatitis B antigen, hepatitis C antibody, and HIV antibody.
- v. To be collected predose and to be performed on serum blood samples.
- w. PK blood samples will be collected predose (within 60 minutes prior to infusion) and 2 hours (± 20 minutes) after initiation of infusion on Day 1 and at Week 13.
- x. Function and strength tests will include the following: Brooke and Vignos scales, PUL, NSAA, and hand-held dynamometer.
- y. PODCI and PARS III Questionnaire.
- z. ActiGraph GT9x will be provided at Screening; 10 hour daytime + full nighttime wear for full study period.
- aa. IP infusion will be administered every week within a ± 3 -day window. A minimum of 3 days (72 hours) should elapse between infusions.
- bb. The chest X-ray will include images of the heart, lungs, airways, blood vessels, and the bones of the spine and chest.

Table 2. Schedule of Study Assessments for Treatment Phase from Week 25 to End of Treatment Phase

Assessment ^a	Treatment Phase (Week 25 to Week 48) ^b ±3 days for each weekly visit														End-of-Treatment Phase		
	25	26 to 28	29	30 to 32	33	34 to 36	37	38 to 40	41	42 to 44	45	46	47	48	49	Follow-up Telephone Call ^c 30 days (±3 days) postdose	ET
General Procedures																	
Medical history ^d	X	X	X	X	X	X	X	X	X	X	X	X	X	X	X	X	X
Height ^e and weight ^f	X						X								X		X
Vital signs ^g	X	X	X	X	X	X	X	X	X	X	X	X	X	X	X		X
Physical and neurological examination ^h	X						X								X		X
12-lead ECG ⁱ	X						X								X		X
Renal ultrasound ^j	X														X		X
Echocardiogram ^k	X														X		X
Laboratory Assessments^l																	
Hematology ^m	X						X								X		X
Chemistry ^m	X						X								X		X
First morning void urinalysis ^{m,n}	X		X		X		X		X		X				X		X
Urine cytology ^o	X						X								X		X
Postdose urinalysis ^{m,p}	X						X										
Anti-dystrophin antibody ^q	X						X								X		
Anti-viltolarsen antibody ^q	X						X								X		
Pharmacokinetic Assessment																	
PK (blood) ^{l,r}	X						X								X		

Assessment ^a	Treatment Phase (Week 25 to Week 48) ^b ±3 days for each weekly visit														End-of-Treatment Phase		
	25	26 to 28	29	30 to 32	33	34 to 36	37	38 to 40	41	42 to 44	45	46	47	48	49	Follow-up Telephone Call ^c 30 days (±3 days) postdose	ET
Other Assessments																	

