6 STUDY POPULATION SELECTION

6.1 Study Population

A target sample size of 20 patients (ambulant and non-ambulant boys, ≥ 8 years of age; a minimum of 8 ambulant patients will be enrolled) with DMD who meet the eligibility criteria below will be enrolled.

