12.2 Determination of Sample Size

Assuming a sample size of 20, at least 1 adverse drug reaction with an incidence of 15% may be detected at a probability of $\geq 95\%$ for the safety profile, which is the primary outcome. Based on this, it was decided that 20 patients should be enrolled to confirm safety. A minimum of 8 ambulant patients will be enrolled.

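### The loss-of-ambulation endpoint does not require that a boy could pass the timed 10-metre test at baseline, so a failure that predates treatment can be classed as a loss on treatment.

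*Combined protocol and SAP*

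**What the plan says.** Section 9.16.1.6 sets the endpoint: "Loss of ambulation will be defined as the inability to perform the Time to Run/Walk 10 Meters Test" in 30 seconds or less, with the failure occurring in "seconds at any post-baseline visit and for all remaining assessments". The same section says that the timed test is done within the NSAA, for those patients who perform it. It does not mention the result before treatment.

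The population is mixed. Section 6.1 takes ambulant and non-ambulant boys, and "a minimum of 8 ambulant patients will be enrolled". Section 6.2 has no walking criterion; function enters only through a Brooke grade of 3 or better, or an FVC of at least 30%.

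The schedule notes in Section 1.2 put the NSAA in the standard battery: "Function and strength tests will include the following: Brooke and Vignos scales, PUL, NSAA, and hand-held dynamometer". No footnote limits it to ambulant boys. Section 9.16.1.5 says that the "total score can range from 0 (completely non-ambulant) to 34 (no impairment").

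The one explicit classification is in Section 9.16.1.3: "Ambulant patients score 1 to 6 and non-ambulant patients score 7 to 10 on the Vignos scale".

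Section 3 lists loss of ambulation as the exploratory endpoint for preservation of ambulation. Sections 12.6.2.1 to 12.6.2.5 describe analyses for the other exploratory measures but none for this one.

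**The concern.** An endpoint meant to show whether walking is preserved needs an at-risk set: the boys who still have the ability at the start. The definition looks only at results after baseline. In a trial confined to boys who can walk this would hardly matter. This trial admits non-ambulant boys by design, so the omission can decide the result.

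Two kinds of boy are affected: a non-ambulant boy who is given the NSAA and cannot do the 10 metres at any visit, and a boy who walks but already takes longer than 30 seconds and never improves. Both meet the wording, although neither has lost anything on treatment.

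The reported proportion would then mix disease status at entry with change on treatment, and it would depend on how many non-ambulant boys were enrolled. The trial is open-label, and Section 12.1 requires the SAP to be final only before database lock. A denominator left open now could therefore be settled after the outcomes are known.

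**Working it through.** **The plan's own figure.** Section 12.2 gives one calculation: "Assuming a sample size of 20, at least 1 adverse drug reaction with an incidence of 15% may be detected" with probability of at least 95%. This is 1 − 0.85^20 = 0.9612, so it reproduces. The smallest number that reaches 95% is 19 (0.9544); 18 gives 0.9464. The calculation concerns adverse reactions and does not depend on the point made here. The documents give no figure for loss of ambulation.

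**Does anything in the text supply a baseline condition?**

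- Section 9.16.1.6 limits timing to patients who perform the NSAA. That is not a requirement to have passed.
- Section 1.2 and the visit lists in Section 10 place the NSAA at Screening, Pre-Infusion, Weeks 13, 25, 37 and 49, and early termination, for every boy.
- Section 9.16.1.4 has a skip rule for weaker boys on the upper-limb scale. Section 9.16.1.5 has no such rule for the NSAA.
- Section 12.3 defines the efficacy population as dosed boys with a baseline and a later efficacy assessment, with no ambulant subset.

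None of these supplies the condition.

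**Who meets the literal rule?** The failure must persist. A boy who fails at Week 13 but passes at a later visit is not classed as lost on the strength of Week 13. A boy who fails at Weeks 13, 25, 37 and 49 is, whatever his result at Screening.

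**Bounds.** Inputs: 20 boys (Section 12.2) and at least 8 ambulant (Section 6.1), so at most 20 − 8 = 12 non-ambulant. Assumptions, none of them stated in the plan: all boys are tested and counted, no data are missing, and no boy who fails at entry later passes. Let A be the number able to pass at entry and k the number of true losses.

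- Literal rule: (20 − A + k)/20
- With a baseline condition: k/A

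| A | k | Literal rule | Baseline condition |
|---|---|---|---|
| 8 | 0 | 12/20 = 60% | 0/8 = 0% |
| 8 | 1 | 13/20 = 65% | 1/8 = 12.5% |
| 8 | 2 | 14/20 = 70% | 2/8 = 25% |
| 12 | 0 | 8/20 = 40% | 0/12 = 0% |
| 16 | 0 | 4/20 = 20% | 0/16 = 0% |
| 20 | 0 | 0/20 = 0% | 0/20 = 0% |

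The two rules agree only when every boy can pass at entry.

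**Would the Vignos grade serve as the at-risk set?** Suppose only 8 boys graded Vignos 1 to 6 are counted, and m of them cannot do 10 metres in 30 seconds at entry or later. With no true loss the literal rule gives m/8: 1/8 = 12.5% for m = 1 and 2/8 = 25% for m = 2, leaving 7 or 6 boys truly at risk. The documents give no value for m.

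**The case against.** The best case against the point is that ordinary language fills the gap. Loss and preservation both presuppose that the boy could walk at the start. Limiting the timed test to boys who perform the NSAA implies that some do not, and Section 9.16.1.5 says that the scale was designed for boys able to walk 10 metres. A score of 0 describes the range of the scale and does not instruct sites to time a boy who cannot walk. The pre-dose results are recorded, so baseline status can be recovered, and Section 12.1 defers detail to a SAP that overrides the protocol and whose separate text is not in the supplied document.

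Much of this stands. Counting baseline failures is what the wording does when applied as written; it is not a stated intention. The NSAA qualifier may also keep some non-ambulant boys out of the count. It does not close the gap, because performing the NSAA does not require passing the 10-metre test. Nor does the text say whether the qualifier applies at baseline or visit by visit. If it applies visit by visit, a boy who truly loses ambulation and stops performing the NSAA might have no timed result.

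A reader might infer that the enrolment minimum and the endpoint use conflicting definitions of ambulant. The documents do not support that: the minimum comes with no definition, and the Vignos sentence is never linked to it. Nor do they say that the minimum of 8 exists to serve this endpoint; in Section 12.2 it sits beside the safety sample size, where "it was decided that 20 patients should be enrolled to confirm safety".

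**Conclusion.** The point holds in a limited form. As written, Section 9.16.1.6 classes a boy who fails before the first dose and at every later assessment as having lost ambulation, and nothing in Section 12 removes him. Using the Vignos grade as the at-risk set would reduce the problem but not fully remove it.

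It would be tempting to read 60% as the expected error. It is only an upper bound when exactly 8 boys can pass at entry. It assumes that the other 12 are tested, that they fail throughout, and that all 20 form the denominator. If non-ambulant boys are not given the NSAA, the excess shrinks to those who are tested and already fail at entry, a number the documents do not give. It would also be wrong to say that one failure at Week 13 settles the classification, because failure must persist at all later assessments.

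The consequence is confined to an exploratory endpoint with no planned control comparison. Within that limit it matters, because this is the only endpoint listed for preservation of ambulation.

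**What to change.** In Section 9.16.1.6 and in the SAP, limit the endpoint and its denominator to patients who completed the timed 10-metre test in 30 seconds or less at baseline. Define baseline as the Pre-Infusion Visit, or Screening if that result is missing; the test is scheduled at both, and the section does not say which applies. List separately any boy graded Vignos 1 to 6 who fails at baseline, so that slow walkers remain visible without counting as losses.

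The cost is a sentence or two in each document. No new assessment is needed, and the change can be made in the SAP even if enrolment is complete, preferably before outcomes are reviewed. The denominator will be smaller, possibly 8 or fewer, so the proportion should be shown with its count. The enrolment minimum needs no change.

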9.17 Pharmacokinetic Assessments

9.17.1 Collection and Assessment of Pharmacokinetic Samples

PK assessments will be performed at visits specified in the Schedules of Study Assessments (Table 1 and Table 2). PK sampling post-infusion times are measured from the start of infusion. Infusion is expected to take 1 hour to complete. Viltolarsen levels in plasma will be assessed at time points for each patient in which anti-viltolarsen antibody is detected. Blood will be drawn from patients for PK analysis at the following sampling times:

- Day 1 (first dose):
 - Predose (within 60 minutes prior to infusion)
 - 2 hours (± 20 minutes) after initiation of infusion
- Week 13:
 - Predose (within 60 minutes prior to infusion)
 - 2 hours (± 20 minutes) after initiation of infusion
- Week 25:
 - Predose (within 60 minutes prior to infusion)
 - 2 hours (± 20 minutes) after initiation of infusion

- Week 37:
 - Predose (within 60 minutes prior to infusion)
 - 2 hours (± 20 minutes) after initiation of infusion
- Week 48:
 - Predose (within 60 minutes prior to infusion)
 - 2 hours (± 20 minutes) after initiation of infusion
 - 6 hours (± 20 minutes) after initiation of infusion

Appropriate PK samples will be collected and processed by a trained member of the study team for shipment to the central laboratory who will forward for analysis. Procedures for the collection, handling, and shipping of laboratory samples will be specified in the Laboratory Manual.

9.17.2 Shipment of Pharmacokinetic Samples

Plasma PK samples will be shipped frozen on dry ice according to instructions provided in the Laboratory Manual.

9.18 Patient Reported Outcomes

9.18.1 Treatment Satisfaction Questionnaire

The TSQM is a self-administered questionnaire that will be used at Week 25 and Week 48. It is a 14-item instrument, yielding 4 subscale scores: global satisfaction, effectiveness, AEs, and convenience.

